## 6.4 Efficacy Assessments

### Tumor Assessment

All measurable and evaluable lesions should be assessed and documented at screening and re-assessed at each subsequent tumor evaluation (see [Appendix A](#)). Assessments should include computed tomography (CT) scans with oral or IV contrast (unless contraindicated) of the chest, abdomen, and pelvis. MRI scans are allowed if CT contrast is contraindicated. Other methods of assessment should be utilized as clinically indicated.

**Tumor assessments for dose escalation cohorts, Dose Expansion Cohort C, Dose Expansion Cohort D, and Dose Expansion Cohort E** are scheduled at Screening and every 8 weeks ( $\pm$ 1 week) thereafter, ie, C3D1, C5D1, C7D1, etc. (odd-numbered cycles).

**Tumor assessments for Dose Expansion Cohort A and Dose Expansion Cohort B** are scheduled at Screening, C2D1, C3D1, C4D1, and every 8 weeks ( $\pm$ 1 week) thereafter, ie, C6D1, C8D1, C10D1, etc. (even-numbered cycles).

Subjects who permanently discontinue study drug for reasons other than progression of disease should continue to be followed for efficacy according to the schedule in [Appendix A](#).

All subjects are to have tumor assessments performed at the Treatment Completion visit, unless the subject was discontinued from treatment because of disease progression or the subject had tumor assessments performed within 14 days of the last dose of study drug.

At the investigator's discretion, CT scans may be repeated at any time if progressive disease is suspected.

Disease status will be assessed using RECIST Version 1.1 (see [Appendix C](#)). The same imaging procedure used to define measurable lesions at baseline must be used throughout the study for each patient.

At the investigator's discretion, other methods of assessment of measurable disease as per RECIST may be used. Examples of other assessment methods include tumor markers, such as prostate-specific antigen (PSA) and cancer antigen 125 (CA-125) levels for patients with prostate and ovarian cancer, respectively. However, tumor markers alone cannot be used to assess response. If markers are initially above the upper normal limit, they must normalize for a patient to be considered in complete response.

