**Appendix A Study Schedule of Events**

Date Procedure	Treatment 											Treatment Completion 	Follow-up
	Screening		Cycle 1				Cycle 2-3		Cycle 4 and onwards				
	Day -28 to Day -1	Day -7 to Day -1	Day 1	Day 8 (±1d)	Day 15 (±1d)	Day 22 (±1d)	Day 1 (±3d)	Day 15 (±3d)	Day 1 of each subsequent cycle (±3d)				
Informed consent 	X												
Tumor assessment (Dose Escalation, Expansion Cohorts C, D, E)	X		Screening, then every 8 (±1) weeks thereafter ( eg C3D1, C5D1, C7D1, etc.)								X 		
Tumor assessment (Dose Expansion Cohorts A and B only)	X		Screening, C2D1, C3D1 C4D1, and every 8 (±1) weeks thereafter (eg C6D1, C8D1, C10D1, etc.)								X 		
Medical history, demographics	X												
Concomitant medication 	X	X	X	X	X	X	X	X	X	X	X	X	
ECOG performance status		X	X		X		X	X	X	X	X	X	
Vital signs 		X	X	X	X	X	X	X	X	X	X	X	
Complete physical examination 		X											
Limited physical examination 			X	X	X	X	X	X	X	X	X	X	
Height	X												
Hematology 		X		X	X	X	X	X	X	X	X	X	

Date Procedure	Screening		Treatment 							Treatment Completion 	Follow-up
			Cycle 1				Cycle 2-3		Cycle 4 and onwards		
	Day -28 to Day -1	Day -7 to Day -1	Day 1	Day 8 (±1d)	Day 15 (±1d)	Day 22 (±1d)	Day 1 (±3d)	Day 15 (±3d)	Day 1 of each subsequent cycle (±3d)	30 (±7) days after permanent treatment discontinuation	Every 12 (±2) weeks from Treatment Completion Visit
Coagulation assay (aPTT, INR)		X		X	X	X	X	X	X	X	
Chemistry panel 		X		X	X	X	X	X	X	X	
Urinalysis 		X		X	X	X	X	X	X	X	
Echocardiogram 	X		X (Every 12 weeks ± 1 week after the first dose)							X	
Thyroid function test 	X						X		X	X	
Serum pregnancy tests 		X								X	
Urine pregnancy tests 							X		X		
Specific tumor markers  Dose Escalation, Expansion Cohorts C, D, E)	X		Screening, then every 8 (±1) weeks thereafter: C3D1, C5D1, C7D1, etc								
Specific tumor markers  Dose Expansion Cohorts A and B only)			Screening, C2D1, C3D1 C4D1, and every 8 (±1) weeks thereafter								
12-lead electrocardiogram 		X	X		X		X		X	X	
PK plasma sampling			PK samples are being collected on Days 1, 2, 14, and 15 of Cycle 1 for Expansion Cohorts B, C, D, and E. Refer to Appendix D for								

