### **Baseline Disease Assessment**

All baseline evaluations should be performed as closely as possible to the beginning of treatment and never more than 4 weeks before the beginning of the treatment.

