16.1.5. PROGRESSION FREE SURVIVAL (PFS)

The PFS is defined as the time from date of first dosing until the date of an objective disease progression as defined by RECIST Version 1.1 (Eisenhauer et al., 2009) or death due to any cause, whichever comes first. More specifically, PFS will be determined using all the assessment data up until the last evaluable visit prior to or on

Document:	[REDACTED]		
Author:	[REDACTED]	Version Number:	2.5
		Version Date:	18Feb2022
Template No.:	[REDACTED]	Reference:	CS_WI_BS005
Effective Date:	02Dec2019		

the date of (i) disease progression as defined by RECIST Version 1.1 or death; or (ii) withdrawal of consent; or (iii) receiving subsequent anti-cancer therapy, whichever is earlier.

The rule of censoring/ event is summarized in Table 1.

The PFS time will always be derived based on scan dates not tumor assessment dates. If PD is documented between scheduled visits, the actual date of documented progression will be used as an uncensored value in the analysis of PFS.

RECIST assessments/scans contributing towards a particular visit may be performed on different dates. The following rules will be applied:

- Date of progression will be determined based on the earliest of the dates of the component that triggered the progression.
- When censoring a patient for PFS the patient will be censored at the latest of the dates contributing to a particular overall visit assessment.

Table 1 Progression free survival

Description	Event/ Censor	Date of Event/Censor
Documented progression before starting use of new anticancer treatment and without missing two consecutive tumor assessment visits	Event	Date of first documented disease progression
Death without progression	Event	Date of death
Progression or death after two or more consecutive missed tumor assessments	Censor	Date of last adequate tumor assessment before two consecutive missed tumor assessment visits
No evaluable baseline tumor assessment	Censor	Date of first dosing of study treatment
No evaluable tumor assessment after first dose of study treatment	Censor	Date of first dosing of study treatment
New anticancer treatment started prior to documented disease progression or death on study	Censor	Date of last evaluable tumor assessment before start use of new anticancer treatment/two consecutive missed tumor assessment visits
No progression and no death before end of study or data cut-off	Censor	Date of last evaluable tumor assessment

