Note: An adequate radiologic assessment is defined as an assessment where the Investigator determined radiological response is CR, PR, SD, or PD. If PD and new anti-cancer therapy occur on the same day, will assume that the progression was documented first, e.g. outcome is progression and the date is the date of the assessment of progression.		

Document: [REDACTED]

Author: [REDACTED]

Version Number:

2.5

Version Date:

18Feb2022

Template No.: [REDACTED]

Reference: CS_WI_BS005

Effective Date: 02Dec2019

Note: Two consecutive scheduled tumor assessments is equal to 126 days (=2* (8 weeks *7+ 7 days)) since previous evaluable RECIST 1.1 or baseline assessment if there is no post baseline tumor assessment.

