Appendix A Study Schedule of Events

Procedure	Date	Treatment ²								Treatment Completion ³	Follow-up	
		Screening		Cycle 1				Cycle 2-3				Cycle 4 and onwards
		Day -28 to Day -1	Day -7 to Day -1	Day 1	Day 8 (±1d)	Day 15 (±1d)	Day 22 (±1d)	Day 1 (±3d)	Day 15 (±3d)			Day 1 of each subsequent cycle (±3d)
Informed consent ¹	X											
Tumor assessment (Dose Escalation, Expansion Cohorts C, D, E)	X		Screening, then every 8 (±1) weeks thereafter (eg C3D1, C5D1, C7D1, etc.)								X ⁴	
Tumor assessment (Dose Expansion Cohorts A and B only)	X		Screening, C2D1, C3D1 C4D1, and every 8 (±1) weeks thereafter (eg C6D1, C8D1, C10D1, etc.)								X ⁴	
Medical history, demographics	X											
Concomitant medication ⁵	X	X	X	X	X	X	X	X	X	X		
ECOG performance status		X	X		X		X	X	X	X		
Vital signs ⁶		X	X	X	X	X	X	X	X	X		
Complete physical examination ⁷		X										
Limited physical examination ⁷			X	X	X	X	X	X	X	X		
Height	X											
Hematology ⁸		X	X	X	X	X	X	X	X	X		
Coagulation assay (aPTT, INR)		X	X	X	X	X	X	X	X	X		
Chemistry panel ⁹		X	X	X	X	X	X	X	X	X		
Urinalysis ¹⁰		X	X	X	X	X	X	X	X	X		
Echocardiogram ¹¹	X		X (Every 12 weeks ± 1 week after the first dose)								X	
Thyroid function test ¹²	X						X		X	X		
Serum pregnancy tests ¹³		X								X		
Urine pregnancy tests ¹³							X		X			
Specific tumor markers ¹⁴ Dose Escalation, Expansion Cohorts C, D, E)	X		Screening, then every 8 (±1) weeks thereafter: C3D1, C5D1, C7D1, etc									
Specific tumor markers ¹⁴ Dose Expansion Cohorts A and B only)			Screening, C2D1, C3D1 C4D1, and every 8 (±1) weeks thereafter									
12-lead electrocardiogram ¹⁵		X	X		X		X		X	X		
PK plasma sampling			PK samples are being collected on Days 1, 2, 14, and 15 of Cycle 1 for Expansion Cohorts B, C, D, and E. Refer to Appendix D for									
			specific timepoints									
Adverse event ¹⁶	X	X	X	X	X	X	X	X	X	X		
Fruquintinib treatment			Once daily, 3 weeks on/ 1 week off									
Survival follow up ¹⁷											X	

Document: [REDACTED]

Author: [REDACTED] Version Number: 2.5
 Version Date: 18Feb2022

Template No.: [REDACTED] Reference: CS_WI_BS005

Effective Date: 02Dec2019

Note:

1. A written informed consent form should be obtained prior to any protocol-specific procedure or test. Tests completed within 28 days prior to enrollment can be used for screening and do not need to be repeated (except hematology, coagulation test, clinical chemistry, or urinalysis results).

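### The single 126-day definition of two missed scans fits only 8-weekly gaps between post-baseline scans; it misclassifies PFS events before C4D1 in Cohorts A and B, and from baseline in the 8-weekly cohorts

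*SAP*

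**What the plan says.** SAP 16.1.5, Table 1, has a censoring row for "Progression or death after two or more consecutive missed tumor assessments". The censoring date is the last adequate assessment before the two missed visits. A note under the table turns the two missed visits into a number of days: "Two consecutive scheduled tumor assessments is equal to 126 days", built as twice the sum of 8 weeks and 7 days, and measured "since previous evaluable RECIST 1.1 or baseline assessment if there is no post baseline tumor assessment". The same note section counts an assessment as adequate only if the investigator's radiological response is CR, PR, SD or PD. No cohort is exempted.

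The scan schedules differ by cohort. Protocol 6.4 gives dose escalation and Cohorts C, D and E a scan every 8 weeks (±1 week). Scans for Cohorts A and B "are scheduled at Screening, C2D1, C3D1, C4D1, and every 8 weeks" after that. Under Baseline Disease Assessment in Protocol Appendix C, the baseline scan may be "never more than 4 weeks before the beginning of the treatment". Protocol 8.5 reads the PFS rate at week 12 for Cohorts B and C and at week 16 for Cohorts D and E.

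**The concern.** The table row counts visits and the note counts days. Where the two disagree, the same patient is an event under one and censored under the other, and the programmer has to choose. There are two such places. Before C4D1 in Cohorts A and B, the scans are closer together than the note assumes. In the 8-weekly cohorts, when there is no post-baseline scan, the clock starts at a baseline scan that can precede first dose by up to four weeks.

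The PFS rate is the primary endpoint of the expansion phase. The PFS definition in Protocol 8.5 has no missed-scan rule, and SAP 2.4 does not list one among the changes from protocol. This footnote alone therefore decides whether these events count.

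**Working it through.** **The plan's own figure.** 2 × (8 × 7 + 7) = 2 × 63 = 126 days. It reproduces.

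**Inputs.** With 28-day cycles, scans in escalation and Cohorts C to E fall on Days 57, 113, 169 and 225. In Cohorts A and B they fall on Days 29, 57, 85, 141, 197 and 253. The baseline scan is k days before Day 1, with k from 1 to 28. I allow ±7 days per scan. Protocol 6.4 attaches ±1 week to the 8-weekly scans, so applying it to C2D1, C3D1 and C4D1 is an assumption on the wide side. I read the cut-off as more than 126 days; the note does not say.

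**Where 126 works.** Between post-baseline scans 8 weeks apart, one missed scan gives 2 × 56 = 112 days (98 to 126) and two give 3 × 56 = 168 (154 to 182). The cut-off separates them. The same holds in Cohorts A and B from C4D1 onward.

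**Cohorts A and B, gaps starting before C4D1.**
- Baseline to C4D1 with C2D1 and C3D1 missed: 84 + k = 85 to 112 days (78 to 119 with windows). This is never above 126, so the event is kept after two missed scans.
- C2D1 to C6D1 with C3D1 and C4D1 missed: 141 − 29 = 112 days (98 to 126). The event is kept. The patient counts as progression-free at week 12 with no scan between Days 29 and 141; Table 1 would censor at Day 29.
- C3D1 to C8D1 with C4D1 and C6D1 missed: 197 − 57 = 140 days (126 to 154). This is censored as Table 1 intends. A death between about Day 149 (after the C6D1 window) and Day 183 (57 + 126) would still count as an event.

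**Escalation and Cohorts C to E, no earlier post-baseline scan.** Week 8 is missed and progression is seen at the week-16 scan.
- On time (Day 113): gap = 112 + k, above 126 when k ≥ 15.
- 7 days early (Day 106): gap = 105 + k, above 126 when k ≥ 22.
- 7 days late (Day 120): gap = 119 + k, above 126 when k ≥ 8.

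Each bound on k falls by one if the cut-off is 126 or more. The 126th day lands between Day 99 (k = 28) and Day 126 (k = 1). SAP Appendix 4 assigns Days 86 to 141 to the week-16 visit in Cohorts C to E, so by the SAP's own windows this patient missed one visit.

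**Effect on the rate** (illustrative rates, no other censoring, patient removed at first dose).
- Event at or before week 16, n = 15: 6/15 = 40.0% becomes 6/14 = 42.9% (+2.9 points); 10/15 = 66.7% becomes 10/14 = 71.4% (+4.8, unrounded); 14/15 = 93.3% becomes 14/14 = 100% (+6.7).
- Event after week 16, n = 15: 6/15 = 40.0% becomes 5/14 = 35.7% (−4.3 points).
- Cohort C at week 12: a gap above 126 days from baseline cannot occur before Day 100, so no week-12 event is lost. Only a week-12 survivor can drop out: 20/40 = 50.0% becomes 19/39 = 48.7%.

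**The case against.** A reader might infer that the rule is wrong for Cohorts A and B throughout, that it censors PFS events at first dose, and that it inflates the PFS rate. The documents support none of these in general.

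- In Cohorts A and B the error is confined to gaps that start before C4D1, and it runs the other way: events are kept that Table 1 would censor.
- Censoring at first dose is not written for the Cohort C to E case. The row points to the last adequate assessment, and a baseline scan is not one. The rows that name first dose cover patients with no evaluable baseline or no evaluable post-dose scan; this patient has both. First dose is the likely fallback, but only by inference.
- The direction depends on timing. Progression on Day 120 falls after week 16, so removing that patient lowers the week-16 rate. Day 113 sits on the landmark: 112 days after first dose, or 113 if a day is added, and the SAP gives no day formula for PFS. A clear rise needs a scan on Days 106 to 112, with k of at least 22 falling to at least 16.
- The Cohort C to E case also needs several conditions together: no earlier post-baseline scan, week 8 missed, progression at week 16 and an early enough baseline scan. The documents give no frequency for this.

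These limits stand. They narrow the point and leave the disagreement between the table row and its note in place.

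**Conclusion.** The concern holds in a limited form. The 126-day figure is correct for 8-weekly gaps between post-baseline scans. For gaps that start before C4D1 in Cohorts A and B it is too lenient, which reaches Cohort B's week-12 rate. From the baseline scan in escalation and Cohorts C to E it is too strict: one missed scan can count as two when the baseline scan is about 15 or more days before dosing (8 to 22 across the scan window).

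Per affected patient in a cohort of 15, the week-16 rate rises by about 3 points at 6/15 and up to about 7 at 14/15 if the lost event was at or before the landmark. It falls if the event came later. In Cohort C at week 12 the effect is small and downward. These sizes assume first-dose censoring and the illustrative rates shown. The change is worth making because the primary endpoint rests on the rule and the remedy is small.

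**What to change.** - Replace the single figure with a count of missed visits by each cohort's own scheduled windows. SAP Appendix 4 has them for Cohorts A/B and C to E; apply the 8-weekly windows to dose escalation as well, which Appendix 4 does not list for tumor scans.
- If a day count is kept, start it at first dose when there is no post-baseline scan. In the 8-weekly cohorts one missed scan then gives at most 120 − 1 = 119 days and two give at least 162 − 1 = 161, so 126 separates them.
- Give Cohorts A and B their own limits before C4D1. With ±7-day windows, the longest gap that one missed scan allows is 64 − 1 = 63 days from first dose, 92 − 22 = 70 from C2D1 and 148 − 50 = 98 from C3D1. From C4D1, 126 stands.
- State whether the cut-off is more than 126 days or 126 days or more.
- State the censoring date when no adequate post-baseline assessment precedes the gap.

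The cost is a rewritten footnote and a short addition to the Appendix 4 windows. No new data are needed.

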16.1.6. OVERALL SURVIVAL (OS)

The OS (in months) refers to the time interval between the first dose date and the date of death (any cause). The last known alive date (i.e. the last follow-up date in patients on study or the date of EOS in patients withdrawn from the study) will be used as the censoring date for patients who have not died at the time of the statistical analysis. Patients lacking data beyond the first dose date will have their survival time censored at the first dose date.

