#### **Early discontinuation of study treatment will occur if any of the following criteria is met:**

1. Patient withdrawal of consent;
2. Intolerable toxicity;
3. Poor patient compliance;
4. Use of other antitumor treatment during the study;
5. Pregnancy occurred during the study treatment period;
6. Patient is lost to follow-up;

7. Treatment discontinuation is in the best interest of the patient based on the assessment of the investigator and the Sponsor.

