### **3.7 End of Study**

End of the study is defined as the last visit of the last patient.

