### **7.1.8.5 Death**

Deaths that occur during the protocol-specified AE reporting period that are attributed by the investigator solely to progression of disease should not be reported as AE/SAE. All other on-study deaths, regardless of relationship to study drug, must be recorded on the AE CRF and immediately reported to the sponsor. When a death is recorded, the underlying condition that caused or primarily contributed to the fatal outcome should be reported expeditiously as an SAE and death listed as the outcome of the event on the CRF. If the primary cause of death is unknown and cannot be ascertained at the time of reporting,

please record “Unknown cause of death” on the AE CRF, and “unexplained/unknown death” should be expeditiously reported as a SAE before further investigations into the specific cause of death. If the death is attributed to progression of disease, it should not be recorded or reported as an AE/SAE but the investigator will record the death on the End of Treatment and End of Study CRFs as appropriate.

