### **Overall Survival (OS)**

Overall survival is defined as the time from the date of the first dose of study drug until the date of death (any cause). Patients who did not die at the time of the statistical analysis will be censored at the time at which they were last known to be alive.

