17. **For subjects in Expansion Cohorts B, C, D, and E** - Survival follow-up (by telephone) should be performed every 12 ( $\pm$ 2) weeks from the date of the Treatment Completion visit. All subsequent anti-tumor therapy and information about ongoing or unresolved study drug-related SAEs will be collected. For the patients that discontinue the study without PD, all available tumor assessment results during survival follow-up will be recorded in the CRF until confirmation of PD. The date and cause of death should be recorded, if applicable. Patients who withdraw consent are encouraged to be followed for survival. If the patient has clearly expressed his/her refusal to be followed after withdrawal of consent, he/she will terminate the study and no survival follow-up will be performed.

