To investigate DLT, 6 DLT-evaluable patients will be firstly enrolled in the phase and will be treated with fruquintinib 3 mg QD (3 weeks on/ 1 week off) orally. If no more than 1 DLT occurs during the DLT observational window (i.e. from Day 1 – 28 in Cycle 1) among the 6 patients, the trial will continue to enroll another 6 patients in the next dose cohort in which fruquintinib 5 mg QD (3 weeks on / 1 week off) will be tested. Safety monitoring and evaluation for the dose escalation phase will be carried out by the Safety Review Committee (SRC). If no more than 1 patient at the dose level of 5 mg QD experiences a DLT, the dose escalation phase is completed, and the expansion phase of the study will be conducted. Upon the completion of the dose escalation phase, the SRC will review aggregated safety and PK data and then select a fruquintinib dose as the RP2D for the expansion phase of the trial. Prior to confirmation of a DLT, if a patient has received any prophylactic medical intervention or missed 4 or more fruquintinib dose during the DLT observational window, the patient is not DLT evaluable and will be replaced. If a patient does not meet the definition of DLT evaluable patient criterion during the DLT observation period, the patient will be replaced. Patients who have completed the DLT observation period (Days 1 – 28, Cycle 1) and are deemed to be benefiting from the fruquintinib treatment at the investigator’s discretion may continue the fruquintinib treatment until disease progression, death, intolerable toxicity, or at investigator’s discretion that the patient can no longer benefit from the study drug.

Patients will be followed until death or study completion, which is defined as the CRF form “End of Study” is filled.

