- If the known part(s) of the AE end date is (are) the same as the death date/ end of study date, the AE end date will be imputed by the death date/ end of study date, whichever occurs earlier.
- In all other cases, the AE end date will be imputed to the last day of the month if only the day is missing or imputed to with 31st December if both day and month are missing.
- If the imputed stop date is before the start date (imputed or non-imputed start date), then the stop date will be imputed using start date.
- If the end date is completely missing or the year part is unknown, the end date will not be imputed.

Here are some examples:

Incomplete AE End Date (DD MMM YYYY)	Date of Death/ End of Study (DD MMM YYYY)	Imputed Date (DD MMM YYYY)
--May2017	Not Available/ Not Available	31May2017
--Sep2017 (known part the SAME as date of death/ end of study)	-----/ 09Sep2017	09Sep2017
----2017 (known part the SAME as date of death/ end of study)	09Sep2017/ 09Sep2017	09Sep2017
--Jun2017 (known part DIFFERENT from date of death/ end of study)	09Sep2017/ 09Sep2017	30Jun2017
-----	-----/ 09Sep2017	-----
31Dec----	09Sep2017/ 09Sep2017	31Dec----
----2018	09Oct2019/ 09Oct2019	31Dec2018

Document: [REDACTED]

Author: [REDACTED]

Version Number:

2.5

Version Date:

18Feb2022

Template No.: [REDACTED]

Reference: CS_WI_BS005

Effective Date: 02Dec2019

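### OS censoring uses an undefined EOS date for patients withdrawn from the study; for patients lost to follow-up it can fall after the last evidence of life and bias OS and follow-up duration upward

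*SAP*

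**What the plan says.** Protocol 8.5 (Overall Survival) says that patients who have not died "will be censored at the time at which they were last known to be alive". It gives no substitute date.

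SAP 16.1.6 keeps the term last known alive date but spells it out as "the last follow-up date in patients on study or the date of EOS in patients withdrawn from the study". It therefore has two classes, on study and withdrawn. SAP 2.4, which lists changes from the protocol, does not mention this.

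EOS is not in the SAP's abbreviation list, and the documents use end of study in two senses:

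- **Patient level.** SAP 2.1 reads "Patients will be followed until death or study completion, which is defined as the CRF form", and the sentence goes on to name the End of Study form and require that it be filled. SAP 6.3.2 sets the date beside each patient's death date: "the AE end date will be imputed by the death date/ end of study date, whichever occurs earlier". Protocol 7.1.8.5 also treats the form as belonging to a patient: "the investigator will record the death on the End of Treatment and End of Study CRFs as appropriate".
- **Trial level.** Protocol 3.7 says "End of the study is defined as the last visit of the last patient".

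On leaving the study, note 17 to protocol Appendix A says that a patient who clearly refuses follow-up after withdrawing consent "he/she will terminate the study and no survival follow-up will be performed". Protocol 3.6 lists "Patient is lost to follow-up" as a separate reason for stopping treatment. Neither document gives an OS censoring rule for that group.

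**The concern.** A censoring date for survival should be a date on which the patient was known to be alive. The filling of a form is not such a date in itself. The End of Study form is also used to record deaths, so its existence does not show that the patient was alive.

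A patient lost to follow-up is no longer on study, so the natural reading of the two-class rule sends that patient to the EOS date. If that date falls after the last contact, the patient stays in the risk set through a period in which a death would not be recorded. The error runs in one direction only: the OS curve goes up and follow-up looks longer.

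The cohorts have no control arm in which a similar error could offset it. Protocol 1.4 presents Cohort C as a US population similar to that of the cited phase 3 study, so a reader may set its OS beside that study's 9.30-month median.

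**Working it through.** **1. Which date is EOS?** SAP usage points to a patient-level date. Section 2.1 ties it to a form, and 6.3.2 compares it with the patient's own death date. The worked examples in 6.3.2 use end-of-study dates of 09Sep2017 and 09Oct2019, well before this SAP version (18Feb2022). The trial-level meaning in protocol 3.7 is therefore the less likely reading, but 16.1.6 does not exclude it.

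**2. Who is affected on the patient-level reading?**

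- Withdrawal of consent with refusal of follow-up: the refusal is a contact with a living patient, so the gap between last contact and EOS is about zero.
- Lost to follow-up: the gap is whatever separates the last contact from the date on the form. The documents do not say how that date is set.

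The paragraph also conflicts with itself at one edge. Its last sentence censors patients with no data after the first dose at the first dose date. A patient lost straight after the first dose who has an EOS form would meet both rules.

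**3. Direction.** The Kaplan-Meier estimate is the product of (1 − d/n) over death times, with d deaths among n at risk. Keeping a lost patient at risk for longer adds to n and cannot add to d, so every affected factor rises. In SAP 16.2, duration to follow-up treats the last date known to be alive as the endpoint and censors deaths. If the EOS date is used there too, a later date lengthens it.

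**4. Size.** The plan gives no precision or event figure for OS, so there is none to reproduce. Its only precision figures, the Clopper-Pearson limits in protocol Tables 15 and 16, were recomputed, and all 12 rows agree to two decimals.

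Inputs for the sizing:

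- Median OS 9.30 months (protocol 1.3.3, cited phase 3 study), assumed exponential. Hazard = ln 2 / 9.30.
- Gap of 10–14 weeks, borrowed from the survival-call interval of 12 (±2) weeks for Cohorts B–E (protocol Appendix A, note 17). At 4.348 weeks per month, this is 10/4.348 = 2.30 to 14/4.348 = 3.22 months.
- Fraction lost: 5%, 10% or 20%. Assumed, because the documents give none.
- Potential follow-up uniform on 6–36 months, and loss independent of survival. Assumed.

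A simulation of 400,000 patients gave these Kaplan-Meier medians in months:

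| Lost | Censored at last contact | Gap 1 month | Gap 10 weeks | Gap 14 weeks | Rise, 10–14 weeks |
|---|---|---|---|---|---|
| 5% | 9.29 | 9.34 | 9.40 | 9.44 | 0.11–0.15 |
| 10% | 9.28 | 9.38 | 9.51 | 9.59 | 0.23–0.31 |
| 20% | 9.29 | 9.51 | 9.79 | 9.97 | 0.50–0.68 |

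Censoring at last contact recovers the true median at every loss rate. The largest shift in the 24-week OS rate with gaps up to 14 weeks is 0.679 − 0.663 = 0.016, at 20% lost.

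**5. The trial-level reading, for contrast.** If every patient who left were censored at the end of potential follow-up, the medians would be 9.60, 9.93 and 10.96 months, a rise of 0.31, 0.65 and 1.67.

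**The case against.** The strongest reply is that the SAP's governing term, last known alive date, already matches the protocol, and that the EOS phrase only says where to find that date. The sentence on patients with no data after the first dose suggests an intent to censor where the data end. The form might itself record the last contact. Withdrawn might not include lost patients, who would then fall under the last follow-up date, which is the right answer. No hypothesis is tested (SAP 5.5), OS is a secondary endpoint, and the cohorts have 6 to 40 patients, so sampling error will usually exceed this bias.

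Much of this stands. The documents do not show how an EOS date is assigned to a lost patient, so the error is possible rather than demonstrated. The 10–14 weeks is a call interval, not a documented gap, and that schedule does not cover dose escalation or Cohort A.

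What does not stand is that nothing needs changing. The parenthesis is a stated rule that equates the two dates for everyone withdrawn, and it neither requires a contact on that date nor says where lost patients belong.

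A reader might infer that the rule overstates OS for withdrawn patients in general. The documents do not support that, because refusal of further follow-up is itself an observation of a living patient. A reader might also infer that forms are closed only after failed contact attempts. No section says so.

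**Conclusion.** The point holds in a limited form. SAP 16.1.6 permits censoring at an undefined EOS date. For patients lost to follow-up that date can be later than the last evidence of life, which departs from protocol 8.5 and can only bias OS and follow-up duration upward. For withdrawal of consent with a patient-level EOS date there is no bias.

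On the assumptions above, the median rises by roughly 0.1 to 0.7 months across loss rates of 5% to 20%, and by nothing if the form date equals the last contact. Larger distortions, up to 1.67 months in the same simulation, need the trial-level meaning of end of study, which SAP 2.1 and 6.3.2 contradict. It would also be wrong to set a 10–14 week gap for one patient beside a 9.3-month median and infer a distortion of that proportion, because only the lost fraction contributes. No test or decision rule is affected. The change is still worth making because the error has a known direction and is easy to remove.

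**What to change.** Replace the parenthesis in SAP 16.1.6 with a rule to this effect: every patient without a recorded death by the time of analysis is censored at the latest date with documented evidence of being alive (visit, dose, scan, laboratory sample or telephone contact); the EOS date counts only if the patient was contacted on that day; the rule applies equally to patients on study, withdrawn and lost to follow-up. Define EOS in the abbreviation list as either the patient-level or the trial-level date. In SAP 16.2, state that duration to follow-up uses the same date.

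The cost is a sentence or two of SAP text and a derivation over dates that the SAP mostly uses already. The one item to confirm against the CRF is that the date of each survival call, and whether the patient was reached, is recorded.
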